Visit 2 (Pre-exercise measurements and exercise protocol, Day 11)

Participants will be assessed actively (including vital signs) at each subsequent visit by study personnel using the side effects/adverse events checklist. Each participant will be read each side effect/adverse reaction from the checklist and instructed to self-report as yes (go) or no (no go). For participants who continue in the study, the following procedures will be performed: completion of psychological questionnaires (FPQ-9, PCS, PASS-20, PSQI, & LEFS), followed by tests of muscle soreness, quantitative sensory testing (QST), the timed stair climbing test (TSCT) and isometric strength measures to evaluate leg function. Participants will then undergo a standardized single bout of eccentric resistance exercise to the dominant quadriceps muscle. An isokinetic dynamometer (Biodex System 4 Pro, Biodex Medical Systems, Inc., Shirley, NY) will be used for the eccentric exercise protocol. Each participant will then perform five sets of twenty-five repetitions. Exercise will be performed using concentric (meaning shortening of muscles during contraction) and eccentric (lengthening of the muscle while still developing tension). The angular velocity will be set at 60°/sec for concentric and 90°/sec for eccentric actions. Participants will be given a three-minute rest period between sets. Each subject will receive \$15 for completing the test session.

Visit 3, 4, & 5 (Follow-up measurements @ 24, 48, & 72-hr post-exercise, Day 12, 13, & 14)
The following procedures will be performed: completion of psychological questionnaires (PCS & LEFS), followed by tests of muscle soreness and leg function testing (TSCT and isometric strength measures). Participants will receive \$5 for completing visits 3, 4 and 5.

Visit 6 (Follow-up measurements @ 96-hr post-exercise, Day 15)

The following procedures will be performed: completion of psychological questionnaires (FPQ-9, PCS, PASS-20, PSQI, & LEFS), followed by tests of muscle soreness, QST, and leg function testing (TSCT and isometric strength measures). At the end of the session each participant will be asked if they thought they were taking the active CBD product or placebo. Participants will receive \$10 for completing visit 6.

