Study personnel will perform a follow-up phone call at 1 week after completion from the study for continued safety monitoring. Study personnel will refer to the checklist to determine if the participant has experienced or is experiencing any side effects or adverse events using the safety monitoring guidelines. If the participant reports experiencing any of the side effects/adverse events from the checklist the study physician will be consulted immediately for guidance and the participant's condition will be followed until full resolution.

Primary Outcome Measures: Self-report ratings of muscle soreness will be used to determine efficacy for duration of soreness and peak intensity of soreness. A muscle soreness inventory will be used to self-report the level of soreness. The muscle soreness inventory consists of rating soreness on a visual analog scale (VAS). A 10cm line is drawn with 0 (no soreness) on the left pole and 10 (extreme soreness) on the right pole. The inventory asks participants to rate their level of soreness by placing a slash on the line that best represents

their current level of soreness and soreness at its worst, best and average over the past 24 hours. The highest worst soreness intensity recorded during the recovery time will be recorded as the peak intensity of soreness. Measures of anxiety and fear of pain/soreness will also be recorded using a similar VAS. **Disability** will be measured using the Lower Extremity Functional Scale (LEFS).³⁷ The LEFS is a self-report questionnaire containing 20 items concerning an individual's ability to perform everyday tasks. The scale can be used to evaluate the functional impairment of a patient post-exercise of one or both lower extremities. Each item includes a 0-4 point hierarchical grading scale with 0 being "extreme difficulty or unable to perform activity" and 4 being "No difficulty". Subjects will rate their level of function for each of the 20 items for a total of 80 points. Each subject's score will be divided by 80 and recorded as a percentage value. LEFS scores will be recorded regularly until recovery and the highest score during this period will be recorded as peak lower extremity disability.

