Participants will be informed during the consenting period, both in writing on the consent form and verbally, that participants will likely experience soreness and stiffness within the exercised muscles after completing the exercise protocol. We postulate that participants will likely experience some level of heightened fear and anxiety (pain-related or other) in the 10-day wash-in phase of the investigational test article before they undergo the experimental exercise protocol and recovery phase. We feel this will be quantifiable on the self-reported psychological questionnaires that the participants will complete before and after the experimental protocol.

Data Management & Analysis

All information and data collected will be stored in locked filing cabinets or in computers with security passwords and accessed only by members of the research team. This process facilitates

data entry and collection, allows for participants to complete self-report questionnaires, and offers optimal security for collecting research-related information. The proposed Data Management will be housed within the Human Performance Laboratory and a secure webbased platform approved by UF (e.g. Redcap) will be used.

Outcome measures will be analyzed using a two-way ANOVA with repeated measures (between-group; within-time) or distribution free test (e.g Friedmans) as indicated by data distribution. Statistical significance will be set at p<0.05. If significant interactions occur, the Tukey post-hoc test will be used to reveal where the differences occur. We will calculate effect sizes and estimates of precision for all outcomes. All data analyses will be performed using SPSS® for Windows 16.0 (SPSS, Inc., Chicago, IL).

A **Data and Safety Monitoring Plan** will consist of two components: (1) overseeing participant safety and data monitoring, and (2) performance of monitoring. Since this project is viewed as low potential risk, all key personnel will perform all data and safety monitoring on an as needed basis.

7. Possible Benefits:

There is no known direct benefit from participating in this study. Study participants have the option of being paid for their time performing research related duties or they may choose to receive extra credit for a course they are currently taking and that may or may not be considered a benefit. There are no other obvious benefits to the study participant.

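### Peak lower extremity disability is defined as the highest LEFS score, but a high LEFS means good function, so the rule records the participant's best visit

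*Combined protocol and SAP*

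**What the plan says.** The relevant text is in section 6, Research Plan, under Primary Outcome Measures. Disability is one of the outcomes there and is measured with the 20-item LEFS.

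- **Item scoring:** a "0-4 point hierarchical grading scale with 0 being 'extreme difficulty or unable to perform activity' and 4 being 'No difficulty". The 20 items sum to a maximum of 80.
- **Conversion:** "Each subject's score will be divided by 80 and recorded as a percentage value". No reversal is stated here or anywhere else in the document.
- **Summary variable:** "LEFS scores will be recorded regularly until recovery and the highest score during this period will be recorded as" peak lower extremity disability.
- **Parallel soreness rule, same section:** "The highest worst soreness intensity recorded during the recovery time will be recorded as the peak intensity of soreness". The soreness scale runs from 0 (none) to 10 (extreme).

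The LEFS is completed at every visit. At Visits 3, 4 and 5 (24, 48 and 72 h) the schedule lists "completion of psychological questionnaires (PCS & LEFS), followed by tests of muscle soreness and leg function testing"; Visits 1, 2 and 6 (Day 1, pre-exercise on Day 11, and 96 h) also include it. Under Data Management & Analysis, "Outcome measures will be analyzed using a two-way ANOVA with repeated measures", with group and time as factors. No separate test is named for the peak variable, but effect sizes and precision are promised for every outcome.

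**The concern.** The label and the rule point in opposite directions. Soreness and LEFS have opposite polarity: the maximum is the worst point for soreness and the best point for LEFS. The same highest-equals-peak rule is applied to both.

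Two things follow for a variable listed among the primary outcomes. First, it measures how far a participant recovered by the end of follow-up, not how disabled the exercise made them. Second, anyone who reads the reported value by its name will reverse the direction of any difference between arms. The study calls itself exploratory, but its estimates are meant to support a larger application, so a reversed peak value could be carried into the planning of that study.

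**Working it through.** **1. Scale.** The plan's own total reproduces: 20 items × 4 = 80. With total T, LEFS% = 100 × T / 80. Every item at 0 gives 0/80 = 0%; every item at 4 gives 80/80 = 100%. Dividing by 80 keeps the direction, so a higher percentage means less disability.

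**2. What the rule returns.** Let disability at a visit be D = 100 − LEFS%. Then, over any set of visits, max(LEFS%) = 100 − min(D). The recorded value is therefore fixed by the participant's smallest disability. The quantity named in the label is max(D) = 100 − min(LEFS%).

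**3. One participant** (assumed scores, attainable on the scale).

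| | 24 h | 48 h | 72 h | 96 h |
|---|---|---|---|---|
| Points | 64 | 59 | 66 | 74 |
| LEFS% | 80 | 73.75 | 82.5 | 92.5 |
| D | 20 | 26.25 | 17.5 | 7.5 |

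The rule records 92.5% as peak disability. The actual peak is 26.25%, at 48 h.

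**4. Severe against mild courses** (assumed).

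| Course (points at 24/48/72/96 h) | Recorded by the rule | Lowest LEFS% | Peak D |
|---|---|---|---|
| Severe, recovers: 50/40/60/80 | 100% | 50% | 50% |
| Severe, incomplete recovery: 50/40/60/74 | 92.5% | 50% | 50% |
| Mild: 72/70/76/80 | 100% | 87.5% | 12.5% |

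A severe and a mild course that both recover by 96 h get the same value. If the severe course does not fully recover, the mild course gets the higher value (100% against 92.5%), so under the label it appears more disabled.

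**5. Which visits count.** The start of the period is not stated. If it is 24 to 96 h, the maximum usually falls at the most recovered visit; the protocol itself expects symptoms to be much reduced within 4-5 days. If the pre-exercise visit is included, the maximum may simply be the uninjured score. Neither is peak disability.

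**6. Illustrative size.** The documents give 15 per arm and a 0.05 significance level, but no LEFS means, SDs, correlations or expected effect. All other inputs below are assumed. Each simulation compares one value per participant with a two-sample t-test, two-sided at 0.05, over 4,000 trials per scenario.

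- *Effect present at every visit.* Vehicle LEFS means 80/74/82/92% at 24/48/72/96 h against 98% before injury; SDs 12/13/11/7; correlation 0.3-0.8; 25-75% of the loss prevented; scores capped at 100%.
- *Effect gone by 96 h.* Vehicle means 58/52/64/76 points; between-subject SD 8 and within-subject SD 4; active arm better by d = 5, 10 or 15 points at 24 and 48 h, d/2 at 72 h and 0 at 96 h; scores capped at 80.

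| Scenario | Arm difference, highest score | Arm difference, lowest score | Power, highest | Power, lowest |
|---|---|---|---|---|
| Effect at every visit | 1.4-4.9 percentage points | 5.1-15.0 | 9-78% | 22-98% |
| Effect gone by 96 h | 0.06-1.3 percentage points | 6.2-17.9 | 5-7% | 32-99% |

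In the first set, the highest score keeps about 27-37% of the arm difference shown by the lowest. In the second it keeps about 1-7% (0.06/6.2 ≈ 1%; 1.33/17.87 ≈ 7%). Varying the first set's SDs by ±25% widens its power ranges to 8-94% (highest) and 15% to above 99% (lowest); the lowest score had more power in all 27 scenarios of that grid. The mean of the four post-exercise scores gave 19-99% at the base SDs, close to the lowest score, so the signal remains in the serial data.

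**The case against.** The best defence is that this is a wording slip carried over from the soreness rule. The item anchors and the label sit beside the rule, so the intent (worst function) is plain and an analyst might notice. The named analysis is a group-by-time repeated-measures ANOVA; one value per participant has no time factor, so no planned test of the peak variable can be identified. The serial scores that would enter the ANOVA are sound. The power figures rest wholly on assumed inputs and move a great deal with the assumed time course, and two-sided power does not speak to a reversed sign.

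Most of this stands, and it limits the consequence. The error touches one derived variable, loses no data, and its effect on power cannot be stated from the documents. It does not remove the contradiction. An analyst who codes the sentence as written takes the maximum, nothing elsewhere reverses the scale, and the variable is listed under the primary outcomes in a plan that promises effect sizes for every outcome. The polarity argument and the worked examples need no simulation.

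**Conclusion.** The definition is wrong as written. On the protocol's own scoring, the recorded value is 100 minus the participant's smallest disability over the period, whichever visits the period covers. In the worked example it reports 92.5% where peak disability is 26.25%. This conclusion rests only on the stated item anchors, the division by 80 and the absence of any reversal.

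The loss of treatment contrast is illustrative: from about two-thirds to nearly all of the arm difference seen with the lowest score, depending on whether an effect is assumed to persist to 96 h. The visit-level LEFS scores and the repeated-measures ANOVA on them are not affected. It should be corrected because it defines a variable listed under the primary outcomes; it does not threaten the trial's data.

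**What to change.** Replace the sentence with: *Disability at each visit is 100 minus the LEFS percentage; the highest disability value at the post-exercise visits (24, 48, 72 and 96 h) is peak lower extremity disability.*

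Alternatively, record the lowest LEFS percentage over those four visits and call it lowest lower extremity function, not disability. The two versions run in opposite directions (26.25% and 73.75% in the worked example), so choose one and use it throughout. In either case, state that a higher LEFS means better function. Naming the four visits also settles where the period starts.

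The cost is one sentence. No new data are needed, because the LEFS is already scheduled at each of these visits; any value already derived under the present rule can be recomputed from the stored scores.

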Aim 2: To determine the impact of sublingual administration of a CBD extract on psychological factors known to influence pain intensity and duration. The investigation of psychological constructs will include evaluating the effects of sublingual administration of a CBD extract on pain-related anxiety, catastrophizing and fear pertaining to participants' views and perceptions toward engaging in strenuous physical exercise, sustaining a musculoskeletal injury and prolonged symptomatic and functional recovery. We hypothesize that the anxiolytic effects of sublingual administration of a CBD extract will diminish the threat and perceived physical stress of exercise-induced pain, physical harm, and prolonged symptomatic and functional recovery.

This exploratory study will provide preliminary data needed to support the hypotheses of a planned larger scale application. Preliminary data will help in better designing a future study aimed at identifying an efficacious dose range of hemp-derived CBD extract, as well as determining the cellular and molecular mechanisms that contribute to symptom resolution and recovery. Our findings may also be helpful for making future improvements for treating a broader range of inflammatory conditions that afflict the musculoskeletal system.

6. Research Plan:

Study Location & Design

The project will involve one study center located on the campus of the University of Florida. Data collection for the study will take place in the Sports Medicine & Human Performance Research Laboratory ([name]). The study protocol will be submitted to the UF Gainesville Health Science Center Institutional Review Board (IRB-01) located in the Gainesville Health Science Center ([name]).

The design will be a double-blind, randomized, vehicle-controlled, three-arm trial. Participants will be randomly assigned to either an active CBD dose group (n=15) or vehicle-control (placebo) group (n=15).. The effects of the active CBD dose groups will be compared to the vehicle-control. Subjects will be required to complete a 15-day study trial spanning a presupplement baseline visit, a controlled daily dosage regimen, pre-exercise baseline testing, eccentric exercise to induce muscle damage, and planned follow-up post-exercise data collection time points.

Study Population

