Inclusion Criteria: a) male and female adults between the ages of 18-35 years and b) English speaking, and c) both female and male subjects must be currently practicing acceptable methods of birth control, such as abstinence, and methods of contraception (barriers, oral, patch or other prophylactic methods).

Exclusion Criteria: (a) use of cannabis products on a regular basis OR positive urine test for cannabis, (b) history of seizure disorder (self or family), traumatic brain injury, liver, kidney, or cardiovascular disease, (c) current medical condition that would prevent the participant from performing strenuous resistance exercise, (d) weight lifting for the lower extremities (legs) more than twice a week, (e) currently experiencing pain in the hips, leg, or knee region, (f) pregnancy, lactating or positive urine pregnancy test, (g) known allergy to CBD, coconut/sesame oil, or tree nuts (coconut).

If the participant self-reports that they are currently using tobacco products or a nutritional/dietary supplement, or if they take prescription anti-depressant/anxiety medications, the participant may continue to use the product(s) but they must be on a stable dose at least 3 months prior to randomization as well as during the 15-day study trial period. Also, if the participant is currently using OTC anti-inflammatory medication (e.g., Advil, Aleve, Aspirin) on a regular basis, we will ask that they stop taking the medication at least 7 days before randomization and refrain from using the product during their participation in the study trial.

Investigational Product & Dosing Schedule

Participants will be provided a 30mL bottle with a syringe dropper on day 1 with instructions to ingest the solution orally using a sublingual route of administration (0.5 cc ~1/2 dropper) twice per day (BID) 12 hours apart (morning and evening) at the prescribed daily dosages: Vehicle-control (0mg/30mL hemp extract = no hemp extract), and active Dose (2000mg/30mL hemp extract = 67mg/day). The sublingual route of administration allows the product to be absorbed directly into venous circulation, and thus bypasses the liver and eliminates the consequences of first pass metabolism; ultimately increasing its bio-availability. The bioavailability of CBD administered orally (including sublingual) is estimated to be 13-19% and its half-life estimated to be around 18-32 hours. 35,36

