Results of urine screening for pregnancy and toxicology (presence of cannabinoids) will be available and assessed during the first visit. If the urine test (pregnancy or cannabinoids) comes back positive, the participant will be excluded from the study. The participant will complete several psychological questionnaires (FPQ-9, PCS, PASS-20, PSQI, & LEFS), followed by tests for muscle soreness and quantitative sensory testing (QST). Each participant will be provided a detailed safety monitoring checklist of side effects and/or adverse reactions that they may potentially experience from ingesting the investigational product. Participants will then be instructed on how to perform their own passive surveillance for identifying these side effects/adverse events and what to do if they experience any of them between study visits while they are ingesting the investigational test article (Days 1 through 10). Participants will be instructed to maintain current activity levels and not to initiate a resistance-training or weightloss program for the duration of the study. Participants will then be randomly assigned to an experimental group and instructed on how to ingest the investigational test article (or placebo) and dosing procedures, which will be dispensed in a quantity to last for the next 15 days. Each participant will be provided a daily log chart to record their daily CBD doses for compliance and monitoring purposes. A pre-exercise visit will be scheduled. Each subject will receive \$10 for completion of the test session.

During the passive surveillance period (Days 1 through 10) participants will be instructed to contact the PI ([name]) if they experience any of the side effects/adverse events from the checklist provided at the baseline visit. [name]/[name] will then contact the study physician ([name]) for consultation. The side effects/adverse reactions will be triaged as mild, moderate or severe, and a determination will be made as to whether the side effect/adverse reaction is due to the investigational product or some other circumstance (e.g. food poisoning). If the event is determined to be due to the investigational test article and graded moderate to severe by the study physician, the participant will then be instructed to stop participation and seek medical care by their primary physician or hospital. Any participant that reports a serious adverse event will be followed to full resolution.

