Maximal Voluntary Isometric Contraction (MVIC) will be measured using the Biodex System 4 Pro (Biodex Medical Systems, Inc., Shirley, NY). MVIC is the maximum voluntary force produced during a static muscle contraction and is a test of leg muscle function. Subjects will be seated with their dominant leg placed in 60° of knee flexion. Each subject will perform three maximal voluntary isometric actions held for 5 seconds. The maximum of the three values will be recorded as peak torque in Newton-meters (N-m).

The Timed Stair Climbing Test (TSCT). To assess physical function and pain with movement, participants will complete a timed stair climb test at baseline and again at follow-up to evaluate functional recovery. Participants will be timed as they ascend (up) and descend (down) a flight of 10 stairs. After completing the trial, the participant will be asked to rate their level of perceived exertion (CR-10 Borg Scale) and level of perceived pain with movement (VAS).

Participants will complete a series of self-report questionnaires to identify their level of anxiety and fear-avoidant behavior patterns prior to completing the experimental injury protocol. The **Fear of Pain Questionnaire** (FPQ-9) is a 9-item, 5-point rating scale to quantify fear of specific situations that normally produce pain.²⁹ The **Pain Catastrophizing Scale** (PCS) is a 13-item, 5-point rating scale used to assess different thoughts that may be associated with experiencing pain.³⁸ The **Pain Anxiety Symptom Scale** (PASS-20) is a 20 item, 5-point rating scale that assesses 4 theoretically distinct components of pain-related anxiety including cognitive anxiety, fear of pain, escape/avoidance behavior, and physiological anxiety.³⁹ The **Pittsburgh Sleep Quality Index** (PSQI) is a self-report questionnaire that assesses sleep quality over a 1-month time interval. The measure consists of 19 individual items, creating 7 components that produce one global score, and takes 5–10 minutes to complete.

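### MVIC is kept in N-m in a mixed-sex sample of 15 per arm with no sex stratum and no sex or baseline adjustment; if strength loss is proportional to strength, the group-by-time test loses some power and is open to chance sex imbalance

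*Combined protocol and SAP*

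**What the plan says.** - **Outcome.** Section 6, Secondary Outcome Measures, takes the best of three isometric efforts: "The maximum of the three values will be recorded as peak torque in Newton-meters (N-m". No scaling to baseline, body mass or a log is mentioned. By contrast, the LEFS score is explicitly converted to a percentage of its maximum.
- **Sample.** Study Population admits "male and female adults between the ages of 18-35 years", with no sex quota or ratio.
- **Allocation.** Study Location & Design gives 15 participants to CBD and 15 to vehicle. Visit 1 says only "Participants will then be randomly assigned to an experimental group". Neither place names a method, blocks or a stratum.
- **Analysis.** Data Management & Analysis states: "Outcome measures will be analyzed using a two-way ANOVA with repeated measures", with group as the between factor and time as the within factor, or a distribution-free test if the data call for it. No covariate is named. "Statistical significance will be set at p<0.05". The result acted on is the interaction: "If significant interactions occur, the Tukey post-hoc test will be used to reveal where the differences occur".
- **Timing.** MVIC is first measured at Visit 2 (Day 11, before exercise, after 10 days of product), then at 24, 48, 72 and 96 h. A pre-exercise value therefore exists, but no adjustment for it is planned.

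**The concern.** Men and women differ in quadriceps strength. If each person loses a similar fraction of strength, a strong participant loses more N-m than a weaker one under the same treatment. A group-by-time test in N-m then treats part of the sex difference as variation in recovery. If one arm happens to hold more men, it shows a larger loss with no treatment effect. With 15 per arm and no stratum, uneven splits are not rare.

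Aim 1 concerns functional as well as symptomatic recovery, the primary outcomes are self-reported, and MVIC is an instrumented measure. The plan promises effect sizes and precision for all outcomes, to inform a larger study. An MVIC estimate shifted by the sex mix would carry into that design.

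**Working it through.** The plan gives no power, SD or effect size for MVIC, so there is no figure to reproduce.

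**Inputs from the protocol:** 15 per arm, alpha 0.05 (two-sided assumed), one pre-exercise and four post-exercise measurements.

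**Assumed inputs, not in the documents:** 15 men and 15 women, and mean pre-exercise MVIC of 250 N-m (men) and 160 N-m (women). Two sets of further assumptions were used:
- Set A: 18% spread within sex, SD 0.15 for log loss, one change score per person.
- Set B: SD 50 (men) and 35 (women) N-m; mean loss 25/22/15/8% at 24/48/72/96 h; SD of loss about 8 points between persons; within-person CV 6%.

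**Step 1: what the interaction sees.** Write MVIC after exercise as b − L, where b is the person's own level and L the loss. The change is −L, so b cancels.
- Additive loss (L the same N-m whatever b is): sex does not enter. In Set B the interaction error mean square was 208.7 with the sex gap and 208.5 without it.
- Proportional loss (L = p × b): with m of the 15 men in the CBD arm and no effect, the arms differ in mean b by (250 − 160) × (2m − 15)/15. For m = 10 this is 90 × 5/15 = 30 N-m. Mean loss over 24 and 48 h is (25 + 22)/2 = 23.5%, so the spurious difference is 30 × 0.235 = 7.05 N-m. Simulation gave 7.0.

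**Step 2: how often the split is uneven.** With 15 men among 30, P(m) = C(15,m)²/C(30,15), and C(30,15) = 155,117,520.
- m = 7 or 8: 2 × 6,435² / 155,117,520 = 53.4%, so a difference of 3 or more men has probability 46.6%.
- m = 6 or 9: 2 × 5,005² / 155,117,520 = 32.3%, so 5 or more has 46.6 − 32.3 = 14.3%.
- m = 5 or 10: 2 × 3,003² / 155,117,520 = 11.6%, so 7 or more has 2.7%.

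If the number of men is itself random (each participant a man with probability 1/2), 3 or more has probability 36%.

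**Step 3: the planned interaction** (Set B, five times, Greenhouse-Geisser, 3,000 trials per scenario).
- Proportional loss, no effect: rejection 4.8% averaged over randomizations, 7.8% at a 10/5 split, 13.5% at 11/4.
- Proportional loss, CBD removing 40% of the loss: power 54%, against 63% had there been no sex gap. Power is 30% with 10 men in the CBD arm and 78% with 5.
- Additive loss, no effect: 4.6% on average, 4.9% at 10/5.

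**Step 4: candidate remedies** (Set B, mean of 24 and 48 h, 4,000 trials; percent of trials rejecting).

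| Scenario | Raw change | Adjusted for pre-exercise MVIC | Same plus sex | Percent of pre-exercise |
|---|---|---|---|---|
| Proportional, no effect, 10/5 | 9.2 | 5.1 | 5.3 | 5.2 |
| Proportional, 40% attenuation, all splits | 55.4 | 71.9 | 70.2 | 76.0 |
| Proportional, 40% attenuation, 10 men in CBD arm | 30.7 | 74.8 | 68.6 | 76.6 |
| Proportional, 40% attenuation, 5 men in CBD arm | 77.8 | 63.0 | 65.1 | 75.9 |
| Additive, no effect, 10/5 | 5.1 | 5.2 | 5.2 | 8.3 |
| Additive, 40% attenuation, all splits | 68.3 | 66.0 | 65.5 | 56.9 |

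Simulation error at 9% is √(0.09 × 0.91/4,000) = 0.45 points.

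**Step 5: Set A.** At a 10/5 split under proportional loss, raw change rejects 9.3%. With sex in the change model, rejection is 4.9% and 4.8% under the two loss models. Log change has more power than raw under proportional loss (80% v 70%) but less under additive loss (67% v 81%), where it also over-rejects at 10/5 (7.1% v 4.5%).

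**Sensitivity.** At 10/5 with proportional loss (Set B), raw change rejects 5.2% if the sex gap is 40 N-m and 10.8% if it is 130 N-m.

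**The case against.** The strongest reply is that a repeated-measures analysis already removes each person's level. A reader might infer that baseline strength differences as such inflate the noise and bias the group-by-time test. They do not: Step 1 shows they cancel unless loss scales with strength. The documents neither state nor exclude such scaling, and give no MVIC mean, SD, loss or sex mix. This part of the reply stands, and the point is conditional on it.

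A reader might also infer that the planned test has an inflated false-positive rate. Averaged over randomizations it does not. The excess appears only given a marked imbalance: at 9/6 under Set A, raw change rejects about 5%. It is also two-sided in effect, since more men in the vehicle arm raises apparent power.

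A third tempting step is to call a log or percent scale a free improvement. It is not. Those scales win when the data are generated as proportional and lose when loss is additive, with the mirror-image distortion under a sex imbalance.

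Finally, the text gives a recording unit and no randomization method. That MVIC will be analysed untransformed and that sex will be ignored in allocation are readings of silence, so the fault is lack of specification. The simulations do not cover the distribution-free alternative. MVIC is also not the only non-questionnaire functional measure, since the timed stair climb is planned too.

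What survives is that nothing in the plan protects MVIC against a plausible form of loss, and cheap protection exists.

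**Conclusion.** The concern holds conditionally. If N-m loss is proportional to pre-exercise strength, the planned interaction loses about 9 points of power to the sex gap (63% to 54% under Set B). Given a 10/5 split of men, false rejection is about 8% for the interaction and 9% for a raw change score. A split that uneven or worse has about a 14% chance if half the sample are men. If loss is additive, neither harm occurs. All the N-m and power figures rest on assumed inputs; only the sample size, alpha, time points and absence of adjustment come from the protocol. The priority is minor, because MVIC is one of several secondary outcomes in a study that calls itself exploratory.

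**What to change.** 1. **Randomization** (Study Location & Design; Visit 1): state the method and stratify by sex, with two short blocked lists.
2. **Analysis** (Data Management & Analysis): for MVIC, include sex as a covariate in a change-score model, or sex-by-time in the repeated-measures model. A sex main effect alone leaves the interaction unchanged. Preferably, also or instead, adjust post-exercise MVIC for the Visit 2 pre-exercise value. In these runs that held rejection near 5% under either loss model. State that this value follows 10 days of product, so the adjustment assumes no product effect on unexercised strength.
3. **Scale:** keep N-m for the main analysis and report percent loss or a log ratio by arm as a sensitivity analysis.

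The cost is a second randomization list, a sentence or two of analysis text, and one or two degrees of freedom. If loss is in fact additive, the price is a few points of power (68.3% to 66.0%, or 65.5% with sex added, under Set B).
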